8.5.1 Reporting Adverse Events

This section describes the responsibilities of site investigators to report adverse events to the study sponsor (DAIT/NIAID) via the DAIT- Statistical and Clinical Coordinating Center (DAIT-SACCC). Timely reporting of adverse events of NCI-CTCAE Grade 2 and higher is required.

Unless otherwise noted below in Section 8.5.2 for serious adverse events and events of special interest, AEs must be recorded on the AE eCRF within five (5) days of discovery of the event. Whenever possible, a diagnosis should be provided, rather than compilation of signs/symptoms, with grade of the event dictated by highest grade of the sign/symptom component.

8.5.2 Reporting of Serious Adverse Events and Events of Special Interest

This section describes the responsibilities of the site investigator to report serious adverse events and events of special interest to the sponsor via the electronic CRF (eCRF). Timely reporting of adverse events is required by 21 CFR Part 312.32, and ICH E6 guidelines.

The adverse events outlined below must be reported by the site investigators to DAIT/NIAID via the DAIT-SACCC regardless of relationship or expectedness to study intervention within 1 business day of discovery of the event:

- All SAEs per 21 CFR 312.32 definitions (see Section 8.2.4, Serious Adverse Events).
- The following events of special interest regardless of drug relationship:
 - o Grade 3 or higher peripheral neuropathy.
 - o Grade 3 or higher neutropenia or thrombocytopenia.
 - o Grade 3 or higher infusion reaction.
 - Anaphylaxis, defined as a serious allergic reaction that is rapid in onset and may cause death (see Appendix 2) [79].
 - New onset rash consistent with Stevens-Johnson syndrome, toxic epidermal necrolysis, or other drug reaction.

- $o = eGFR < 30 \text{ ml/min/1.73m}^2$.
- o Potential drug-induced liver injury, defined as all three of the following:
 - ALT or AST elevation > 3 times ULN, and
 - Total bilirubin > 2 times ULN, without initial findings of cholestasis (elevated serum alkaline phosphatase), and
 - No other immediately apparent possible causes of ALT or AST elevation and hyperbilirubinemia, including but not limited to viral hepatitis, pre-existing chronic or acute liver disease, or the administration of other drugs known to be hepatotoxic.
- o Grade 3 or greater infection.
- A suspected case of PML.
- All other Clinical events with an NCI-CTCAE Grade 3 or greater severity deemed possibly or definitely related to brentuximab vedotin.

Note: clinical events include signs/symptoms, diagnoses, and laboratory abnormalities with clinical consequence (defined as the requirement for intervention, correction, increased monitoring, or further evaluation).

When a site investigator identifies a serious adverse event or event of special interest specified above, he or she must notify DAIT/NIAID via the DAIT-SACCC within 1 business day. Site investigators are to report these events on the SAE eCRF in EDC. Should EDC become unavailable/ inaccessible, the site investigator should notify DAIT/NIAID via the DAIT-SACCC email at [contact]. This email can serve as the initial notification; however, within the next business day the SAE eCRF must be completed.

All requested information on the SAE eCRF should be provided. Unavailable details of the event at time of initial report should not delay submission of known information. The initial report should include at a minimum: AE term, relationship to brentuximab vedotin, and reason why event is serious (per definitions). Supplementary CRF pages including medical history, concomitant medications, demographics, study drug administration, and death must be provided. As additional details become available, the SAE eCRF should be updated and submitted. With each iteration of the form, the investigator (or designated sub-investigator) must sign the form electronically.

For additional information regarding SAE reporting, contact Rho Product Safety (DAIT-SACCC):

Rho Product Safety [name] Toll-free-([contact] SAE Fax Line: [name]

Email: [contact]

8.6 REPORTING TO HEALTH AUTHORITIES

After an adverse event requiring 1 business day reporting (per Section 8.5.2, Reporting of Serious Adverse Events of Special interest) is submitted by the site investigator and assessed by DAIT/NIAID, there are two options for DAIT/NIAID to report the adverse event to the appropriate health authorities (Annual Reporting and Expedited Reporting).

8.6.1 Annual Reporting

DAIT/NIAID will include in the annual study report to health authorities all adverse events classified as:

- Serious, expected, suspected adverse reactions
- Serious and not a suspected adverse reaction
- Pregnancy

Note that all adverse events (not just those requiring 24-hour reporting) will be reported in the Annual IND Report.

8.6.2 Expedited Safety Reporting

This option applies if the adverse event is classified as one of the following:

- Serious and unexpected suspected adverse reaction [SUSAR]:
 - A single occurrence of an event that is uncommon and known to be strongly associated with drug exposure
 - One or more occurrences of an event that is not commonly associated with drug exposure, but is otherwise uncommon in the population exposed to the drug
 - An aggregate analysis of specific events observed in a clinical trial that indicates those events occur more frequently in the drug treatment group than in a concurrent or historical control group

The sponsor (DAIT/NIAID) will notify the appropriate health authorities (FDA) and all participating investigators of Expedited Safety Reports within 15 calendar days; unexpected fatal or immediately life-threatening suspected adverse reaction(s) will be reported as soon as possible or within 7 calendar days.

Final Study Report: A complete summary of safety information (including both Standard and Expedited reports as defined above) is included in the final study report to be submitted to both US FDA at the closure of the protocol.

8.7 REPORTING OF ADVERSE EVENTS TO IRBS

All investigators shall report AEs and SAEs, including IND safety reports, in a timely fashion to their respective IRBs in accordance with applicable regulations and guidelines.

8.8 REPORTING PREGNANCY

The investigator shall be informed immediately of any pregnancy in a study subject or a partner of a study subject. A pregnant subject shall be instructed to stop taking study medication. The investigator shall counsel the subject and discuss the risks of continuing with the pregnancy and the possible effects on the fetus. Monitoring of the pregnant subject shall continue until the conclusion of the pregnancy.

The investigator shall report to the sponsor (DAIT/NIAID) via the DAIT-SACCC any pregnancy in a study subject or a partner of a study subject within one business day of becoming aware of the event according to the procedures specified in section 8.5.2. The pregnancy eCRF will be used to submit the information for tracking purposes only, as the pregnancy itself is not considered an SAE. All pregnancies identified during the study shall be followed to conclusion and the outcome of each must be reported. The Pregnancy information must be updated and submitted to the DAIT-SACCC via the eCRF form as new information becomes available. When possible, similar information should be obtained for a pregnancy occurring in a partner of a study subject.

Information requested about the delivery shall include:

- Gestational age at delivery
- Birth weight, length, and head circumference
- Gender
- Appearance, pulse, grimace, activity, and respiration (APGAR) score at 1 minute, 5 minutes, and 24 hours after birth, if available
- Any abnormalities

All pregnancy complications that result in a congenital abnormality, birth defect, miscarriage, and medically indicated abortion should be submitted on the SAE eCRF form.

Mycophenolate REMS Program. It is strongly recommended that investigators with female participants of childbearing potential taking mycophenolate mofetil (MMF) enroll them in the Mycophenolate Risk Evaluation and Mitigation Strategy (REMS) program (www.mycophenolaterems.com). Under this program, an investigator will be required to report any pregnancy occurring in a female participant while she is taking MMF or within the first 6 weeks following discontinuation of MMF treatment to the Mycophenolate Pregnancy Registry, which

is part of the MMF REMS program. Study participants will be encouraged to participate in the MMF REMS program as well.

8.9 REPORTING UNANTICIPATED PROBLEMS

An investigator must promptly notify the sponsor (DAIT/NIAID) via the DAIT-SACCC if an "unanticipated problem involving risks to subjects or others" is identified, which is not otherwise reportable as an adverse event.

8.10 REVIEW OF SAFETY INFORMATION

8.10.1 Medical Monitor Review

The DAIT/NIAID Medical Monitor shall receive monthly reports from the DAIT-SACCC compiling new and accumulating information on AEs, SAEs, and pregnancies recorded by the study site(s) on appropriate eCRFs.

In addition, the Medical Monitor shall review and make decisions on the disposition of the SAE and pregnancy reports received from the DAIT-SACCC.

8.11 DATA SAFETY AND MONITORING BOARD REVIEW

8.11.1 Routine DSMB Reviews

The progress of the study will be monitored by the NIAID Data and Safety Monitoring Board (NIAID DSMB). The NIAID Autoimmune DSMB will be chartered to review safety data and to make recommendations to NIAID regarding continuation, termination, or modification of the study. The DSMB will review the safety data 6 months after the first participant is treated. Following the initial review, the DSMB will review the safety data at least yearly during planned DSMB Data Review Meetings. Data for the planned safety reviews will include, at a minimum, a listing of all reported AEs and SAEs.

The DSMB chair will be informed of any Expedited Safety Reports in a timely manner in order to make a recommendation for an ad hoc full board review and /or protocol suspension. Discontinuation of study treatment will also be periodically reported to the DSMB. In addition, safety data will be reviewed by the DSMB when an event occurs that is of sufficient concern to the NIAID medical monitor or protocol co-chairs to warrant review, or when an event occurs that could contribute to a stopping rule.

8.11.2 Protocol-Defined Interim Safety Reviews

Interim safety reviews will be undertaken by a Safety Review Committee (SRC) comprised of a subgroup of the DSMB. The study design (section 3.1) specifies interim safety analysis and review by the SRC after each of the first two dosing cohorts have completed 12 weeks of therapy. Approval by the SRC is required following review of the 12-week interim safety data prior to proceeding to the next higher dosing cohort.

Interim safety analysis will also be conducted after each of the first two dosing cohorts have completed 24 weeks of therapy.

Following each protocol-specified interim safety review, the SRC can recommend actions regarding study conduct, including, but not limited to, the following:

- 1. Continue the study as planned.
- 2. Add participants to an existing dosing cohort.
- 3. Reduce the number of weeks of study drug administration for the next higher dosing cohort.
- 4. Stop the study.

8.11.3 Ad hoc DSMB Reviews (Stopping Rule Guidance)

If any of the following events occur, the chair of the DSMB will be notified and a review of the safety data will be performed. The DSMB will have the discretion to recommend actions regarding study conduct, and will determine if enrollment in the study should be stopped and/or administration of investigational study medication should be halted:

- 1. Any death that is at least possibly related to use of the investigational study medication.
- 2. Any life-threatening infusion reactions during infusion of study medication or within the observation period after study medication that lead to permanent discontinuation of the infusion, including anaphylaxis.
- 3. One case of PML.
- 4. Any grade 4 adverse event that is at least possibly related to use of the investigational study medication.
- 5. Two or more Grade 3 or higher peripheral neuropathy events involving different participants.

If stopping rule 1, 2, or 3 is met, then no new participants will be consented, and no new participants will be enrolled, until after the DSMB completes review of the safety data. Participants in the screening phase of the study may continue to undergo minimal risk procedures.

If stopping rule 4 or 5 is met, the study will proceed as planned pending DSMB review of the data. However, if two weeks has elapsed and the DSMB has not met, then no new participants will be consented, and no new participants will be enrolled, until after the DSMB completes review of the safety data.

In the event that a temporary halt is placed on consent and enrollment, participants already enrolled in the study will continue to receive study medication if they are not the subject of the DSMB review.

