Although serious infections were not common in the pivotal phase II trials, one participant in an early dose finding study died after developing febrile neutropenia and sepsis. This participant received 3.6 mg/kg brentuximab vedotin (twice the dose that was subsequently approved) [46]. Other fatal infectious adverse events included influenzal pneumonia and cytomegalovirus infection [65]. Pneumocystic carinii pneumonia has also occurred [65]. Although rare, PML has been reported in 5 individuals receiving brentuximab vedotin [67, 68], resulting in the addition of a black box warning for PML to the prescribing information [55]. The incidence of PML in cancer patients treated with brentuximab vedotin was < 0.05% [65].

In the phase III trial of brentuximab vedotin as consolidation therapy following high dose immunotherapy and autologous stem cell transplantation for refractory HL, serious

infections were reported in 15 participants (9%) in the brentuximab vedotin arm and 7 participants (4%) in the placebo arm, with pneumonia as the most common serious infection [65]. Herpes simplex and herpes zoster infections occurred more commonly in the brentuximab vedotin arm, while other opportunistic infections were rare. Overall, in the pivotal studies serious infections were reported in 10% of patients. Treatment-related serious adverse events included pneumonia, urinary tract infection, staphylococcus bacteremia, and pneumocystis carinii pneumonia. Grade 1 or Grade 2 upper respiratory infection was the infection with the highest incidence [65].

In a phase III trial of brentuximab vedotin compared to physician's choice of methotrexate or bexarotene for CD-30 positive cutaneous T cell lymphoma, serious infectious adverse events related to study drug occurred in 4 participants. These included Grade 3 impetigo, Grade 3 diverticulitis, and Grade 3 cellulitis [65]. All three serious infectious adverse events resolved without sequelae. One participant in each arm of the trial had infectious adverse events associated with Grade 3 or Grade 4 neutropenia.

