5.2 TOXICITY MANAGEMENT OF BRENTUXIMAB VEDOTIN

5.2.1 SARS-CoV-2 Infection or Exposure

Suspend brentuximab vedotin or placebo administration if the participant develops symptomatic or asymptomatic SARS-CoV-2 infection:

- Participants with mild or moderate SARS-CoV-2 infection should be evaluated for treatment with a monoclonal antibody product authorized by the FDA for the treatment of COVID-19, as soon as possible following confirmation of the infection and within 10 days of symptom onset [69-71]. Use of other FDA authorized or approved therapeutic agents should also be considered as they become available, depending on the clinical circumstance.
- Brentuximab vedotin may be restarted at the next scheduled dose, if symptoms have been absent for at least 10 days, or in the case of asymptomatic infection at least 10 days have passed since the positive SARS-CoV-2 test. In addition, a negative PCR test for SARS-CoV-2 must be obtained prior to restarting brentuximab vedotin or placebo administration.
- Any participant who has close contact with a SARS-CoV-2 infected individual should be evaluated for post-exposure prophylaxis as soon as possible after exposure [69, 70].

Version 5.0

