5.2.4 Permanent Discontinuation of Study Medication for Toxicity

Permanently discontinue brentuximab vedotin if any of the following occurs:

- The participant misses > 3 doses of brentuximab vedotin.
- Grade 2 peripheral neuropathy recurs after brentuximab vedotin suspension and dose modification, as described above.
- Grade 3 or greater peripheral neuropathy.
- Grade 3 or greater neutropenia or thrombocytopenia.
- Grade 3 or greater infusion reaction.
- Anaphylaxis, defined as a serious allergic reaction that is rapid in onset and may cause death (see Appendix 2) [79].
- New onset rash consistent with Stevens-Johnson syndrome, toxic epidermal necrolysis, or other drug reaction.
- eGFR $< 30 \text{ ml/min}/1.73 \text{ m}^2$.
- Potential drug-induced liver injury, defined as all three of the following:
 - o ALT or AST elevation > 3 times upper limit of normal (ULN), and
 - Total bilirubin > 2 times ULN, without initial findings of cholestasis (elevated serum alkaline phosphatase), and
 - No other immediately apparent possible causes of ALT or AST elevation and hyperbilirubinemia, including but not limited to viral hepatitis, preexisting chronic or acute liver disease, or the administration of other drugs known to be hepatotoxic.
- Two or more Grade 3 or greater infections, or one Grade 4 infection.

• A suspected case of PML.

A diagnosis of PML should be considered in any participant presenting with new-onset or deteriorating neurological signs and symptoms. The participant should be referred to a neurologist or other appropriate specialist for evaluation. If PML is suspected, this should be immediately reported to the NIAID Medical Monitor. The appropriateness of continuing study medication, while the case is being assessed, should be discussed.

If brentuximab vedotin is discontinued, the procedures in Section 4.3 should be followed.

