8.2.3 Unexpected Adverse Event/Reaction

A SAR is considered "expected" when it is listed in the investigator brochure, the package insert, or the protocol. A SAR is considered "unexpected" when its nature (specificity), severity, or rate of occurrence is not consistent with applicable product information as described in the safety information provided in the investigator brochure, the package insert, or the protocol (21 CFR 312.32(a) and ICH E2A). A serious unexpected suspected adverse reaction is referred to as a SUSAR. For this study, expectedness will be determined by product information provided in the investigator brochure, package insert, and protocol for brentuximab vedotin.

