9. STATISTICAL CONSIDERATIONS AND ANALYTICAL PLAN

9.1 ANALYSIS SAMPLES

9.1.1 Analysis Populations

The safety sample is defined as all subjects who receive any amount of the placebo or the brentuximab vedotin study drug. They will be summarized and compared according to the treatment actually received. Because participants receive their assigned medication on the day of randomization, this is conceptually equivalent to the standard intention to treat analysis population.

Supplementary per protocol (PP) analysis samples are defined as follows:

- PP12: Treated participants who receive at least 4 of the 5 infusions over the first 12 weeks, and who have no major protocol deviations that would affect the safety outcomes through the first 12 weeks.
- PP24: Treated participants who receive at least 7 of the 8 infusions over the first 21 weeks, and who have no major protocol deviations that would affect the safety outcomes through the first 24 weeks.
- PP36: Treated participants who receive at least 7 of the 8 infusions over the first 21 weeks, and who have no major protocol deviations that would affect the safety outcomes through the first 36 weeks.
- PP48: Treated participants who receive at least 7 of the 8 infusions over the first 21 weeks, and who have no major protocol deviations that would affect the safety outcomes through the first 48 weeks.

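### After a possibly related death or a PML case, Section 8.11.3 stops enrollment but keeps dosing everyone else until the DSMB decides, with no review deadline; a short default hold would be safer and costs little

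*Protocol*

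**What the plan says.** Section 8.11.3 lists five events that bring the safety data to the DSMB. Rule 1 is a death at least possibly related to study medication, rule 2 a life-threatening infusion reaction, rule 3 a single PML case, rule 4 a possibly related grade 4 event, and rule 5 grade 3 or higher neuropathy in two participants.

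For the first three, the automatic consequence concerns people not yet in the trial: "If stopping rule 1, 2, or 3 is met, then no new participants will be consented, and no new participants will be enrolled" until the board has finished its review. For those already in the trial, the last paragraph of the section says that during such a halt "participants already enrolled in the study will continue to receive study medication if they are not the subject of the DSMB review".

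Whether dosing stops is left to the DSMB as a result of the review. The only time limit in the section, two weeks, belongs to rules 4 and 5, where it triggers an enrollment halt if the board has not met. Rules 1 to 3 carry no time limit for the review.

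**The concern.** The sentence about enrolled participants is a stated rule, so it is not a detail that a charter or analysis plan would fill in. After either of these two events, people who have not been exposed are kept out. People who are being exposed receive whatever infusion falls due before anyone has judged whether dosing is still acceptable.

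The enrollment halt does useful work while a cohort is filling, and it keeps the next cohort from opening. Once Cohort 3 (1.8 mg/kg) is fully enrolled, it reaches only replacement participants under Section 4.5.

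The usual argument for continuing treatment, expected benefit, is weak here. Section 1.4.2 tells participants not to count on personal benefit, and a hold leaves the background immunosuppression of Section 5.3.1.1 in place. At stake are avoidable infusions of an antimitotic antibody-drug conjugate, in a non-oncology dose-escalation trial, while a death or a PML case is still unexplained.

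**Working it through.** The plan gives no figure on this point. The check is therefore a comparison of sections, followed by short arithmetic on exposure and cost.

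**1. Does anything else hold the other participants' infusions by default?**

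- **4.3:** the investigator or medical monitor may stop an individual's treatment. This is discretionary.
- **5.2.4:** a suspected PML case stops drug permanently, but only for that participant.
- **8.5.2 and 8.10.1:** one-business-day reporting and medical monitor disposition of SAE reports. These are fast, but no dosing consequence is attached.
- **8.11.1, first route:** the chair is told of Expedited Safety Reports "in order to make a recommendation for an ad hoc full board review and /or protocol suspension". This leads to a recommendation, not an automatic hold. Such reports cover serious unexpected suspected reactions (8.6.2). Under 8.2.3 a reaction counts as expected "when it is listed in the investigator brochure, the package insert, or the protocol", unless its nature, severity or rate does not fit the product information.
- **8.11.1, second route:** the DSMB reviews data when an event worries the medical monitor or co-chairs, or could contribute to a stopping rule. The review can start early, but dosing continues meanwhile.

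No section sets a default hold.

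**2. Exposure during a pending review**

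Infusions are given every 3 weeks, which is 21 days (3.1). If the review begins at a random point in a participant's cycle and infusions remain, the expected number falling due in d days is d/21. The review lengths are assumptions.

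| Assumed review | As written | With a hold |
|---|---|---|
| 7 days | 7/21 = 0.33 | 0 |
| 14 days | 14/21 = 0.67 | 0 |
| 21 days | 21/21 = 1.0 | 0 |

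These are averages per other participant still on treatment.

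**3. Cost of a hold**

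- Infusions are at least 18 days apart (6.1.2). Since 14 < 18, a hold of up to 14 days can catch at most one infusion per participant, leaving 7 of 8 (87.5%).
- The per-protocol thresholds in 9.1.1 are 4 of 5 infusions for PP12 and 7 of 8 for the later samples, for example "PP48: Treated participants who receive at least 7 of the 8 infusions over the first 21 weeks". A participant with no other missed infusion still qualifies.
- Two missed infusions leave 6 of 8, below the PP24, PP36 and PP48 threshold. That could happen if the participant had already missed one, or if the hold outlasted one dosing interval (18 to 21 days).
- The safety sample needs only some study drug to have been received, so it is unaffected.
- Permanent discontinuation applies when "The participant misses > 3 doses of brentuximab vedotin". One held infusion is far from that.

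**The case against.** The strongest reply is that this is a deliberate choice and no error. The section is labelled as guidance. It separates new exposure, which stops automatically, from ongoing exposure, which the board decides. Chair notification and review are mandatory, the board may halt dosing, and suspected PML goes to the medical monitor immediately. All of this is correct. It lowers the severity, but it does not change what happens to an infusion that falls due before the decision.

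A second reply concerns false alarms. Rule 1 needs only a possible relation, judged first by a blinded investigator (6.2.2, 8.3.3), in a disease for which Section 1.1 gives 55% mortality at 10 years. With 6:2 allocation, 2 of every 8 participants receive placebo, so a disease death on placebo could hold a cohort. This stands. It is the reason for a target date and for allowing the decision to use unblinded assignment.

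Several stronger readings are tempting, but the documents do not support them:

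- **That nobody can stop dosing before the board meets.** Sections 4.3 and 8.11.1 give several people the means. What is missing is a default.
- **That PML necessarily escapes the chair's suspension route because it is a listed reaction.** Under 8.2.3 a rate out of line with product information makes a reaction unexpected, so the route may open.
- **That one case would show the next infusion to be dangerous, because Section 1.4.1.2 states that** "The incidence of PML in cancer patients treated with brentuximab vedotin was < 0.05" **per cent.** That figure comes from cancer patients. A confidence limit around one observed case does not measure the added risk of one further infusion.
- **That Section 5.2.1 is a precedent, because it says** "Suspend brentuximab vedotin or placebo administration if the participant develops symptomatic or asymptomatic SARS-CoV-2 infection". It suspends the infected participant only, not unaffected ones.
- **That a cohort total of infusions can be stated.** It depends on an unknown dosing calendar. If all had just been dosed, none would fall due for at least 18 days.

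**Conclusion.** The concern holds as a design improvement. After a possibly related death or a PML case, the default is continued dosing of everyone except the subject of the review, with no review deadline, and every other safeguard is discretionary or covers only the affected participant. Reversing the default for these two triggers is proportionate, because the gain is avoided exposure during the most uncertain period and the cost is small.

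The size is d/21 infusions per other on-treatment participant in a d-day review, or 0.33 to 1.0 over the assumed 7 to 21 days, against none with the hold. This rests on an assumed review length, a random starting point in the cycle and infusions still to come. It does not measure harm per infusion, which the document gives no basis to estimate. Sample size and the primary analysis in the safety sample are unchanged.

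**What to change.** In the last paragraph of 8.11.3, for rules 1 and 3 only, substitute:

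> The next infusion of every other participant at the same or a higher dose level is held until the DSMB, or its chair on its behalf, recommends in writing that dosing may continue. This interim recommendation is to be sought within 14 days and may use unblinded treatment assignment. Infusions held under this rule do not count toward the > 3 missed doses in 5.2.4 or toward replacement in 4.5.

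Keep the present text for rules 2, 4 and 5.

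The costs are these:

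- A hold of up to 14 days costs each participant at most one of eight infusions.
- A longer hold, or a hold for someone who has already missed an infusion, could remove that participant from a per-protocol sample, but not from the safety sample.
- A possibly related death on placebo could trigger a hold. The unblinded look lets the chair release it early. Section 6.2.3 requires ITN and NIAID approval for unblinding in unplanned analyses that support DSMB reviews, so that approval is best agreed in advance.
- The hold covers both arms of a cohort, so the hold itself does not reveal any participant's assignment.
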